The enucleation technique is nearly similar in both groups regardless of the energy source used, a 26 Fr continuous flow resectoscope (Karl Storz, Germany) with saline irrigation. The procedure will start by incision along the deepest prostatic groove using a bilobed technique where each lobe will be enucleated separately or a trilobed technique to separate a huge median lobe first then to continue as bilobed technique, the incision continues till verumontanum, then we will perform a circumferential marking proximal to the external urethral sphincter for demarcation, lateral incision will be done till the prostatic capsule and start enucleation using a mechanical force of the resectoscope with assisted energy source either Holmium laser or bipolar electrocautery, and then we will proceed anterolateral around the prostatic adenoma, aiming for early apical separation to avoid traction of the external sphincter with mucosal strip to be left intact more proximal to avoid dissemination of energy to the sphincter, anterior commissurotomy to be done to separate each lobe separately the procedure mimic figure enucleation in open surgery by using the resectoscope assisted energy source and then to proceed anteriorly till the bladder neck and then we complete the enucleation from anterior to lateral and move downward to finally separate the adenoma from posteriorly into the bladder, in this way we avoided the sub-trigonal injury or ureteric injury, then we perform the other lobe in the same way, after separation of each lobe we check the ureteric orifices and adequate hemostasis was done, finally morcellator will be used to cut down prostatic adenoma into small chips to be removed.

Inclusion criteria: Men who are fit for surgery and need a surgical resection of the prostate larger than 80 ml including:

1. Bothersome LUTS with an IPSS score over 19
2. Refractory hematuria
3. Upper urinary tract affection
4. Recurrent UTI secondary to prostatic enlargement
5. Maximum uroflow rate (Qmax) below 10 ml/sec.

6. bladder diverticula
7. Urinary retention whether recurrent acute attacks with failure of medical treatment or chronic retention.

Exclusion criteria: Patients with:

1. Neurogenic bladder
2. Previous prostate or urethral surgery
3. Associated urethral stricture
4. Prostate cancer diagnosed by TRUS biopsy
5. Bladder stones,

Ethical Considerations: Approval will be obtained from the ethical committee at Ain shams University before starting the research.

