Study Procedures: The patients will undergo the following:

Preoperative:

1) History:

Including medical history, surgical history, drug history, International Prostate Symptom Score (IPSS) and quality of life score (QoL).

2) Clinical Examination:

Including abdominal, pelvic and digital rectal examination (DRE).

3) Laboratory investigations:

As Haemoglobin level, serum creatinine, urea, sodium, potassium and prostate specific antigen (PSA).

4) Radiological investigations:

As pelvi-abdominal ultrasound to assess prostate volume and postvoiding residual urinary volume (PVR).

5) Maximum Flow Rate (Qmax).

Intraoperative: Vital data monitoring, operative time and the need for blood transfusion

Postoperative Follow-up Protocol:

Patients will be evaluated immediately postoperative with vital signs (Blood pressure, Heart rate), abdominal examination, degree of haematuria, haemoglobin level drop and Sodium level changes.

Patients will be re-evaluated at 6 and 12 months postoperatively with the IPSS, QoL, Pelvic U/S (to assess prostate volume and post voiding residual urinary volume (PVR)) ,

Maximum Flow Rate (Qmax) and Total PSA .

Data collection and outcome measures:

Primary outcomes:

1. Catheter removal time

Secondary Outcomes:

1. Operative time, enucleation time
2. Intraoperative need of blood transfusion and hemoglobin drop
3. Conversion to other type of surgeries
4. Post-operative drop in hemoglobin level
5. Duration of hospital stay
6. Postoperative complication: urinary tract infection, stress incontinence, hematuria, urine retention
7. Post voiding residual urine, Qmax, PSA, Prostate volume, QoL and IPSS 1 and 12 months postoperative
8. Delayed complication up to 12 months postoperative including urethral stricture, urinary retention, incontinence or bladder neck contracture.
9. Cost effectiveness of each procedure.

Statistical Analysis: The data will be collected, processed and statistically analyzed. Description of the quantitative variable will be done as mean and standard deviation and student t-test will be used to compare the two groups in parametric data while the qualitative data will be shown as frequency and compared using Chi square test. The results will be considered significant with P-value less 0.05 and high significant if less than 0.01, results with P-value ≥ 0.05 will be considered non-significant. Analysis of the data will be done using IBM SPSS software (Statistical program for social science version 21).

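### Optional precision gain for secondary outcome 7: the plan specifies no use of the preoperative IPSS, QoL, Qmax, PVR, PSA and prostate volume when the arms are compared at follow-up

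*Combined protocol and SAP*

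**What the plan says.** All references are to the combined protocol and SAP.

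- **Preoperative list (Study Procedures).** IPSS and QoL are taken with the history, PSA with the laboratory tests, prostate volume and PVR by ultrasound, and Qmax as a separate item.
- **Secondary Outcomes, item 7.** The same six measures return: "Post voiding residual urine, Qmax, PSA, Prostate volume, QoL and IPSS 1 and 12 months postoperative".
- **Postoperative Follow-up Protocol.** The visit list has different times: "Patients will be re-evaluated at 6 and 12 months postoperatively with the IPSS". Only 12 months appears in both places.
- **Statistical Analysis.** Quantitative variables are described by mean and SD, and "student t-test will be used to compare the two groups in parametric data". No covariate, regression model or change score is named, and no test is given for quantitative data that are not parametric.
- **Follow-up value or change.** The plan does not say which is compared for item 7. Elsewhere it names a change when it means one, as in "haemoglobin level drop and Sodium level changes". Item 7 therefore reads most naturally as follow-up values, but this is inference.

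**The concern.** Item 7 carries much of the efficacy part of the stated aim. The trial already plans to collect a preoperative value for each of the six measures. Where that value predicts the follow-up value, adjusting for it narrows the confidence interval for the difference between arms at no cost in data. With about 40 men per arm at follow-up, the precision could be useful.

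Leaving the choice between follow-up value and change unstated also lets the analysis be settled after the data are seen, and the two choices can differ considerably in power.

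**Working it through.** **The plan's own figure.** The only sample size given is 50 per group, for catheter removal time. From its inputs (means 1.3 and 3.8, SDs 0.6 and 1.7, alpha 0.05 taken as two-sided, power 90%), the pooled variance is (0.36 + 2.89)/2 = 1.625. Then n = 2 × (1.960 + 1.282)² × 1.625 / 2.5² = 5.5, so 6 per group, or 8 after 20% dropout. The stated 50 is not reproduced. That is a separate matter, and nothing below depends on it. The plan sets no power target for item 7.

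**Inputs.**
- Evaluable men per arm: 50 × (1 − 0.20) = 40, from the Sample size paragraph.
- Two-sided 5% test, normal data (assumed).
- Baseline/follow-up correlation ρ from 0.1 to 0.6 (assumed; not in the documents).
- Comparator: t-test on follow-up values at 80% power (our yardstick).

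**Step 1, reference.** With 78 df, the noncentral t gives 80% power at a difference of 0.634 SD. The 95% CI half-width is t × √(2/40) = 0.445 SD.

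**Step 2, baseline-adjusted regression.** The variance relative to the t-test is (1 − ρ²) × (1 + 1/76), with 77 df. The second term is the cost of estimating the slope. The last column is a t-test on change scores with equal SDs, variance factor 2(1 − ρ), 78 df.

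| ρ | Variance factor | Power, adjusted | CI half-width (SD) | Power, change score |
|---|---|---|---|---|
| 0.1 | 1.003 | 79.9% | 0.446 | 55.1% |
| 0.2 | 0.973 | 81.1% | 0.439 | 60.1% |
| 0.3 | 0.922 | 83.1% | 0.428 | 65.8% |
| 0.4 | 0.851 | 85.9% | 0.411 | 72.5% |
| 0.5 | 0.760 | 89.5% | 0.388 | 80.0% |
| 0.6 | 0.648 | 93.6% | 0.359 | 87.9% |

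Break-even is where (1 − ρ²) × 1.0132 = 1, that is ρ = 0.114.

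**Step 3, restricted baseline range.** Entry is limited to "Men who are fit for surgery and need a surgical resection of the prostate larger than 80 ml", which truncates baseline prostate volume for everyone. The IPSS and Qmax limits are read as alternative indications and restrict only part of the sample. QoL, PSA and PVR have no direct limit. If entry keeps a fraction of a normal baseline with variance ratio u, the correlation becomes ρ√u / √(ρ²u + 1 − ρ²). The difference is held at 0.634 SD of the enrolled men's follow-up values.
- Upper three quarters (u = 0.535): ρ of 0.1 to 0.6 becomes 0.07 to 0.48; power 79.7% to 88.8%.
- Upper half (u = 0.363): ρ becomes 0.06 to 0.41; power 79.6% to 86.3%.

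**Step 4, missing baselines.** Men in retention are eligible and may lack a usable baseline Qmax, IPSS or PVR (assumed). With a share m missing, a constant filled in and an indicator added, the factor is (1 − (1 − m)ρ²) × (1 + 2/75), with 76 df.
- m = 0.3: power 79.2% to 89.2%; break-even ρ = 0.19.
- m = 0.5: power 79.1% to 86.3%; break-even ρ = 0.23.

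**Step 5, both together (ρ 0.1 to 0.6 before restriction).**
- Upper three quarters, m = 0.3: power 79.1% to 85.5%; break-even ρ = 0.26.
- Upper half, m = 0.3: power 79.0% to 83.8%; break-even ρ = 0.31.
- Upper half, m = 0.5: power 79.0% to 82.4%; break-even ρ = 0.36.

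**The case against.** The strongest reply is that this is a preference. Randomisation makes the unadjusted t-test valid, catheter removal time has no baseline value to adjust for, item 7 is one of nine secondary items, and no wrong conclusion is identified. All of that stands, and it limits the point to an optional improvement.

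The benefit also rests on a correlation that the documents do not supply. Across the assumed range the result runs from a trivial loss to a clear gain, and at 0.2 the gain is 1.1 points of power. This stands too: nothing in the plan shows where any of the six measures lies in that range, and restricted or missing baselines can remove most of the gain.

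A reader might infer that the preoperative values are left out of every comparison. The text does not support that. If changes were tested, the baselines would be used and the power figures for the adjusted analysis would need a different comparator. What can be said is that no use is specified.

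Finally, the t-test applies only to data judged parametric. For a measure that is not, the plan names no test, so the t-test is not the plan's comparator and these figures, which assume normal data, do not describe it.

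**Conclusion.** The point holds as an optional gain in precision for secondary outcome 7. It would be wrong to read it as a flaw in the t-test, as a threat to the primary outcome, or as a promise of a large gain.

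Against an 80% yardstick with 40 men per arm, adjustment gives essentially nothing at correlations of 0.1 to 0.2, about 3 points of power at 0.3, and 9.5 points at 0.5. With restricted and partly missing baselines combined, the best case examined is 85.5%. The worst case is small: at zero correlation, power falls to 79.5%, or to 78.9% with the indicator. The correlations, degrees of restriction and missing shares are all assumptions.

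A further benefit does not need a high correlation: writing the model down settles whether follow-up values or changes are compared. At a correlation of 0.3, for example, a t-test on changes would have 65.8% power against 83.1% for the adjusted analysis, if the two SDs are equal.

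**What to change.** Add to the Statistical Analysis section, before any outcome data are examined:

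1. For each of the six measures in item 7, the 12-month follow-up value is compared by linear regression on arm plus the same measure's preoperative value. The adjusted difference is reported with its 95% CI.
2. Where a preoperative value is missing, for example in men in retention, a constant is filled in and a missing-baseline indicator is added. This keeps men who have follow-up data from being lost for lack of a baseline. It does nothing for missing follow-up.

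Twelve months is used because both lists name it. The conflict between 1 and 6 months for the earlier visit must be reconciled separately.

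Two extras are optional and lie outside this fix. A log scale for PSA and PVR changes the quantity estimated from a mean difference to a ratio, so it should be chosen on its own merits. Adjusting haemoglobin for its preoperative value is likewise a separate choice.

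The cost is a few sentences and a few regressions in the software already named, with no new data. The statistical cost at a correlation near zero is about 1.3% of variance, or 2.7% with the indicator.
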